8.3 SUBJECT DEATH

8.3.1 Procedure for recording and reporting subject death

All subject deaths are to be documented and reported to the sponsor within 72 hours after becoming aware of the event.

In event of subject's death a death and a withdrawal form should be completed. Deaths should be classified according to primary cause (cardiac, non-cardiac, unknown) and relationship to the protocol and or device. Adverse event form should be completed if appropriate.

9.0 DATA MANAGEMENT

Overall, the Sponsor will be responsible for the data handling.

The sponsor and/or its affiliates will be responsible for compiling and submitting all required reports to governmental agencies.

Data will be analyzed by the Sponsor and may be transferred to the Sponsor's locations outside of Europe and/or any other worldwide regulatory authority in support of a market-approval application.

St. Jude Medical respects and protects personally identifiable information that we collect or maintain. As part of our commitment, St. Jude Medical is certified to the U.S. - European Union Framework and U.S. – Swiss Safe Harbor Framework Agreements regarding human resources and subject clinical trial personal information. The privacy of each subject and confidentiality of his/her information will be preserved in reports and when publishing any data. Confidentiality of data will be observed by all parties involved at all times throughout the clinical study. All data will be secured against unauthorized access.

The following documents will be produced and maintained as part of this study:

- Informed consent form
- CRFs

The Principal Investigator or institution will provide direct access to source data during and after the clinical study for monitoring, audits, IRB/EC review and regulatory authority inspections. As required, the Principal Investigator or institution will obtain permission for direct access to source documents from the subject, hospital administration and national regulatory authorities before starting the clinical study.

9.1 DATA MANAGEMENT PLAN

A detailed Data Management Plan will be established to ensure consistency of the data. This document will include procedures used for data review, database cleaning, and issuing and resolving data queries. If appropriate, the DMP may be updated throughout the study duration. All revisions will be tracked and document controlled.

CRF data will be captured in a validated electronic database management system hosted by St. Jude Medical.

Clinical Investigational Plan

All CRF received data for the study will be entered by trained and qualified St. Jude Medical personnel. An electronic audit trail will be used to track any subsequent changes of the entered data.

9.2 DOCUMENT AND DATA CONTROL

9.2.1 Traceability of documents and data

The investigator will ensure accuracy, completeness, legibility and timeliness of the data reported to the sponsor on the CRFs and in all required reports.

9.2.2 Recording data

Source documents will be created and maintained by the investigational site team throughout the clinical study.

The data reported on the CRFs will be derived from, and be consistent with, these source documents, and any discrepancies will be explained in writing.

The following data can be recorded directly in the CRFs:

- Pain VAS scores
- EQ-5D scores
- ODI scores

The CRFs will be signed and dated by the authorized site personnel. Any change or correction to data reported on a paper CRF will be dated, initialed and explained if necessary, and will not obscure the original entry.

10.0 MONITORING

It is the responsibility of St. Jude Medical as the sponsor of the study to ensure the study is conducted, recorded, and reported according to the approved protocol, subsequent amendment(s), applicable regulations, and guidance documents. Monitoring will be conducted according to the St. Jude Medical Clinical Monitoring standard operating procedure.

Prior to beginning the study, St. Jude Medical will contact the investigator or designee to discuss the study and data requirements. A St. Jude Medical monitor will periodically review the subject records and associated source documents.

The investigator shall make subject and study records available to the clinical monitor for monitoring.

11.0 REGULATORY INSPECTIONS

The investigator and/or delegate should contact St. Jude Medical immediately upon notification of a governmental agency inspection at the site. A clinical monitor or designee will assist the investigator and/or delegate in preparing for the audit.

Clinical Investigational Plan

An investigator who has authority to grant access will permit authorized governmental agency employees, at reasonable times and in reasonable manner, to enter and inspect any establishment where devices are held (including any establishment where devices are used or where records or results are kept).

An investigator, or any person acting on behalf of such a person with respect to the study, will permit authorized governmental agency employees, at reasonable times and in reasonable manner, to inspect and copy all records relating to the study.

An investigator will permit authorized governmental agency employees to inspect and copy records that identify subjects, upon notice that governmental agency has reason to suspect that adequate informed consent was not obtained, or that reports required to be submitted by the investigator, to the Sponsor or IRB/EC have not been submitted or are incomplete, inaccurate, false or misleading.

12.0 STATISTICAL CONSIDERATIONS

12.1 STATISTICAL DESIGN, HYPOTHESES, METHOD AND ANALYTICAL PROCEDURES

VAS scores, EQ-5D scores and ODI scores will be tested for statistical differences using a repeated measures ANOVA .

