4.4.2 Secondary Endpoint

- Comparison of subject preference between the 2 lead implantation techniques during the SCS trial
- Changes in low back and lower limbs pain between baseline and at 3, 6 and 12 months after permanent implant (evaluated using Visual Analog Scale (VAS) assessments)
- Changes in quality of life assessed using the EQ-5D questionnaire and in disability assessed using the Oswestry Disability Index (ODI) between baseline, trial assessments and at 3, 6 and 12 months after permanent implant
- Evaluate subject satisfaction at 3, 6 and 12 months after permanent implant

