6.2 PROCEDURES

The clinical study will be conducted in accordance with the CIP. All parties participating in the conduct of the clinical study will be qualified by education, training, or experience to perform their tasks and this training will be documented appropriately.

The clinical study will not commence until St. Jude Medical receives written approval from the IRB/EC and relevant regulatory authorities and all required documents have been collected from the site(s).

Table 1: List of all study specific activities/procedures

Visit Study Activity	Enrollment	Baseline Screening	SCS Trial	Trial Assessment 1	Trial assessment 2	SCS Implant procedure	Activation	Follow up Visits*
Informed Consent Process	X							
Inclusion/Exclusion Criteria Screening	X							
VAS assessment		X		X	X			X
EQ-5D questionnaire		X		X	X			X
ODI questionnaire		X		X	X			X
Provide pain diary			X	X			X	X
Collect pain diary				X	X			X
Subject Preference questionnaire						X		
Trial leads implant			X					
EPG programming			X	X				
Permanent implant							X	
IPG Programming								X
Subject Satisfaction questionnaire								X

* Follow up visit assessments will be performed after activation visit at weeks 12 (84±7 days), 26 (182±7 days), and 52 (365±7 days).

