6.15 CRITERIA AND PROCEDURES FOR SUBJECT WITHDRAWAL OR DISCONTINUATION

Subjects must be informed about their right to withdraw from the study at any time and for any reason without sanction, penalty or loss of benefits to which the subject is otherwise entitled and withdrawal from the study will not jeopardize their future medical care or relationship with the investigator. Subjects will be asked to specify the reason for the termination, but have the right not to answer.

The investigator may decide to withdraw a subject from the study at any time with reasonable rationale. The subject's future care will not be influenced by a decision, voluntary or otherwise, to withdraw from the study. All reasonable efforts should be made to retain the subject in the clinical study until completion of the study.

Reasons for subject's withdrawal include, but are not limited to:

- Subject refuses to continue participating in the study
- Subject does not meet the inclusion/exclusion criteria and does not require additional follow-up for safety reasons.
- Subject is deceased (cause must be documented)
- Subject's non-compliance
- Subject's participation is terminated by the PI or investigator, although the subject consented, since participation is no longer medically appropriate

Clinical Investigational Plan

- Subject is 'lost to follow up': Subject does not adhere to the scheduled follow up visits but has not explicitly requested to be withdrawn from the clinical study. (This does not apply to missed visits). Site personnel should at all times make all reasonable efforts to locate and communicate with the subject in order to achieve subject compliance to the scheduled follow up visits:
 1. A subject will be considered 'Lost to Follow Up' after a minimum of 2 phone calls of a physician or delegate at the investigational site to the subject or contact. These 2 phone calls need to be documented in the subject's hospital records.
 2. If these attempts are unsuccessful, a letter should be sent to the subject's last known address or general practitioner (GP) and a copy of this letter should be maintained in the subject's hospital records.

Note: If a subject misses one or more of the scheduled follow up visits (inclusive of the assigned visit windows), this will be considered as a missed visit. The subject may therefore still return for subsequent visits and will not be excluded from the study.

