12.2 SAMPLE SIZE

Approximately 50 patients will be enrolled in this study. Based on clinical experience atleast 80% of the subjects are expected to have a successful trial and be implanted with permanent IPGs. Enrollment will be discontinued after 40 subjects have received a permanent implant. This study is a feasibility trial; the sample power cannot be calculated because the effect size is not known. The sample size was selected to obtain early evidence and estimates of the effect size.

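### Run in its classical form, the repeated measures ANOVA in section 12.1 would drop from the 3, 6 and 12 month analysis subjects whom section 6.15 keeps in the study

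*Combined protocol and SAP*

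**What the plan says.** Section 12.1 is a single sentence: "VAS scores, EQ-5D scores and ODI scores will be tested for statistical differences using a repeated measures ANOVA". It does not list the visits in the model, the model terms, the analysis set, the method of estimation or the handling of missing values. No other section supplies these.

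The long-term outcomes are secondary endpoints. Section 4.4.2 includes "Changes in low back and lower limbs pain between baseline and at 3, 6 and 12 months after permanent implant", and lists EQ-5D and ODI changes at the same visits. The note under the activity table in section 6.2 places the visits at days 84, 182 and 365 after activation, each with a window of 7 days either side.

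Section 6.15 judges a missed follow-up visit with the visit windows taken into account. It separates missed visits from loss to follow-up ("This does not apply to missed visits") and says of a subject who misses one or more: "The subject may therefore still return for subsequent visits and will not be excluded from the study".

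On numbers, section 12.2 says "Approximately 50 patients will be enrolled in this study" and "Enrollment will be discontinued after 40 subjects have received a permanent implant".

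**The concern.** The classical repeated measures ANOVA needs a full set of values for each subject. If baseline and all three follow-up visits enter one such analysis, a subject who misses the 6 month visit is removed at 3 and 12 months as well, although those scores were recorded. Section 6.15 foresees exactly this kind of subject and keeps collecting data from them. Over a year, with windows of only 7 days either side, some gaps are likely.

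Two things are at stake. The first is precision: section 12.2 says the sample was chosen to give early evidence and estimates of effect size, and 40 subjects leave little to spare. The second is possible bias: if missing a visit is related to pain, the subjects with complete data no longer represent all those implanted.

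**Working it through.** **Inputs from the documents.** About 50 enrolled, at least 80% expected to have a successful trial, and 40 implanted (section 12.2); three follow-up visits (section 6.2). The plan's own figure reproduces: 50 × 0.80 = 40.

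**Assumed input.** The documents give no rate of missed visits. Let q be the chance of missing any one follow-up visit, independent across visits and subjects, with baseline always present. The range used is 5% to 20%.

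**Step 1: loss of subjects and data.**
- Subjects with all three visits: 40(1 − q)³.
- Follow-up assessments recorded: 40 × 3 × (1 − q) = 120(1 − q).
- Assessments kept by a complete-case analysis: 3 × 40(1 − q)³.
- Discarded: the second quantity minus the third.

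| q | Complete subjects (share of 40) | Recorded | Kept | Discarded |
|---|---|---|---|---|
| 5% | 34.3 (86%) | 114 | 102.9 | 11.1 |
| 10% | 29.2 (73%) | 108 | 87.5 | 20.5 |
| 15% | 24.6 (61%) | 102 | 73.7 | 28.3 |
| 20% | 20.5 (51%) | 96 | 61.4 | 34.6 |

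**Step 2: precision at 12 months.** Subjects with a 12 month score number 40(1 − q): 38, 36 or 34 at 5%, 10% or 15%. With the same SD in both sets, the standard error of the complete-case 12 month change, relative to one using everyone with a 12 month score, is √[40(1 − q) / 40(1 − q)³] = 1/(1 − q). That is 1.05, 1.11 or 1.18, so the standard error is 5%, 11% or 18% larger even when missing visits are unrelated to pain.

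**Step 3: direction of any bias.** This was checked by simulating 400,000 subjects with three follow-up visits, a true mean VAS of 3.0 at each, SD 2 and correlation 0.6. The first visit was always observed. The other two were each missed by about 10%, with a chance that depended on the first score. All these values are assumptions.

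| Who misses visits | Complete-case mean VAS at the three visits |
|---|---|
| Unrelated to pain | 3.00, 3.00, 3.00 |
| Worse pain misses more | 2.67, 2.80, 2.80 |
| Less pain misses more | 3.33, 3.20, 3.20 |

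The bias is therefore zero, favourable or unfavourable according to who misses.

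**Step 4: does a mixed model recover the means?** In a sample of 4,000 under the worse-pain pattern, the full-data means were 2.95, 3.01 and 2.98. Complete cases gave 2.62, 2.80 and 2.78. A random-intercept mixed model on all available visits gave 2.95, 3.02 and 2.98. Missingness here depended only on an observed score, so the data were missing at random by construction, which suits the mixed model. The result does not show how it performs when missingness depends on the unseen score.

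**The case against.** The strongest reply is that section 12.1 never says subjects with a missed visit are dropped. Deletion is a property of the classical method as usually run. The term is also used loosely for a likelihood-based mixed model, and separate contrasts of baseline with each visit would lose a subject only from the contrast concerned. This stands: the plan does not state deletion. But it does not state any alternative either, and the method it names, taken at face value, is the one that needs complete data.

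A reader might infer that the long-term results will be tilted towards subjects doing well and so overstate relief. The documents do not support that. They give no reason for missed visits and no indication of which subjects miss them, and step 3 shows that the sign can go either way. Nor can a firm size of bias be given, because it depends on assumed miss rates and an assumed pain level.

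A reader might also see a contradiction between sections 6.15 and 12.1. There is none. Section 6.15 is a rule of conduct, compatible with any analysis set. What is missing is a rule that links it to the analysis.

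Finally, the stakes are limited. The primary endpoint rests on baseline and the two trial-phase assessments, before the visits at issue. The study is a feasibility trial, and section 6.14 provides for monitoring of retention. All this lowers the priority. It does not justify discarding recorded data when the alternative is easily available.

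**Conclusion.** The point holds as a cheap improvement. As worded, section 12.1 permits an analysis that would discard attended visits from retained subjects. At assumed independent miss rates of 5%, 10% or 15% per visit, about 34, 29 or 25 of the 40 implanted subjects would remain. At 10%, about 21 of 108 recorded assessments would go unused, and the 12 month standard error would be about 11% larger than with all available 12 month scores.

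This rests on three assumptions: that the ANOVA is run in its classical form, that baseline and all three follow-up visits enter one model, and that the miss rates are as assumed. Bias is possible in either direction, and the documents establish neither its presence nor its sign. The loss of precision alone is enough reason to change the method. Only the secondary long-term endpoints are affected.

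**What to change.** For VAS, EQ-5D and ODI at 3, 6 and 12 months, replace the ANOVA in section 12.1 with a mixed model for repeated measures fitted by REML, and state the following:

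- The analysis set is all implanted subjects, with every available visit used and no one removed for a missed visit.
- Visit is a categorical factor with baseline and the three follow-up visits as levels.
- The covariance is unstructured, with a named simpler structure as the fallback if the model does not converge.
- The change from baseline at each visit is reported with its 95% CI.
- The analysis assumes that data are missing at random.
- One sensitivity analysis covers data missing not at random, for example by shifting the unobserved scores by a range of amounts in both directions, since the sign is unknown.

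If a mixed model was intended all along, the same text makes that clear.

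The cost is plan wording, standard software and slightly more analysis work, with no new data and no change to conduct. The one practical risk is non-convergence: an unstructured covariance over four time points has 4 × 5 / 2 = 10 parameters to estimate from about 40 subjects, which is why the fallback should be fixed in advance.

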12.2 SAMPLE SIZE

Approximately 50 patients will be enrolled in this study. Based on clinical experience atleast 80% of the subjects are expected to have a successful trial and be implanted with permanent IPGs. Enrollment will be discontinued after 40 subjects have received a permanent implant. This study is a feasibility trial; the sample power cannot be calculated because the effect size is not known. The sample size was selected to obtain early evidence and estimates of the effect size.

12.3 PASS/FAIL CRITERIA TO BE APPLIED TO THE RESULTS OF THE CLINICAL STUDY

The trial will be considered successful if significant pain relief can be obtained using burst stimulation in leads implanted using anatomical midline-based lead positioning.

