4.0 STUDY DESIGN

4.1 PURPOSE

The primary purpose of this study is to compare the therapeutic efficacy of the conventional, paresthesia mapping-based burst SCS implant strategy to a more novel, anatomic midline-based approach that has the potential to streamline the workflow associated with the SCS treatment continuum.

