4.2 STUDY DESIGN AND SCOPE

This study is a prospective, multicenter, single-blinded feasibility study consisting of two phases: SCS trial and permanent implant follow up.

Patients recommended by the Principal Investigator as a candidate and who meet the standard requirements will be approached to participate in this study. Patients that meet the inclusion/exclusion criteria and sign the informed consent will be enrolled in the study and undergo baseline assessment to collect primary and secondary outcome measures prior to the SCS trial. Specifically, assessments will include pain ratings as assessed by visual analog scale (VAS), quality of life as assessed by the EQ-5D and disability as assessed by the Oswestry disability index (ODI).

Subjects will subsequently undergo a SCS trial using the St. Jude Medical (SJM) Invisible Trial system. During the trial implant, two SCS leads will be implanted using standard surgical techniques. One lead will be implanted using paresthesia mapping to maximize the overlap between painful regions and evoked paresthesia according to standard clinical practice. A second lead will be implanted using a novel anatomical midline-based approach. Under fluoroscopic guidance, the lead will be positioned above the anatomical midline such that it extends over the T9-T10 junction.

Subjects will be randomized 1:1 to receive burst stimulation using one of the 2 leads (lead placed using paresthesia mapping or lead placed by anatomic midline-based approach or vice versa), and will be blinded to the randomization order.

The SCS trial will consist of two phases, and will last for a total of 4 weeks.

During the first trial phase, burst SCS will be delivered for two weeks using the first lead in the randomization sequence. After two weeks, subjects will assess the pain level, quality of life and disability associated with stimulation delivered.

Clinical Investigational Plan

Subjects will then cross over to the second trial phase during which burst stimulation will be delivered for an additional two weeks using the second lead in the randomization sequence.

At the end of the second trial phase, subjects will assess pain level, quality of life and disability associated with stimulation delivered using the second lead. Subject preference for stimulation delivered during the two trial phases will also be recorded during this visit.

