4.3 OBJECTIVES

4.3.1 Primary Objective

- Compare pain relief provided by paresthesia mapping-based burst trial to anatomical midline-based burst trial

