4.5.1 Inclusion Criteria

- Subject is able to provide informed consent to participate in the study;
- Subject is 18 years of age or older;
- Subject has failed to respond to at least 6 months of conventional treatment including pharmacological treatment, physical therapy, epidural injections and/or radiofrequency therapy as per NICE Tag 0159;
- FBSS subjects with predominant low back pain;
- Subject has a low back and pain intensity of at least 6.0 out of 10.0 on the VAS at baseline;
- Subject is on stable pain medications with a total opioid equivalent of 120 mgs a day or less for at least 28 days prior to enrolling in this study, and is willing to stay on those medications with no dose adjustments until activation of the permanently implanted SCS device;
- Subject's medical record has been evaluated by the Investigator to ensure that the subject is a good candidate for a neurostimulation system;

Clinical Investigational Plan

- Subject is willing to cooperate with the study requirements including compliance with the regimen and completion of all office visits;
- Female candidates of child-bearing potential agree to commit to the use of an effective method of contraception (including but not limited to sterilization, barrier devices, oral contraceptives, intrauterine devices (IUDs), condoms, rhythm method, or abstinence) for the duration of the study

Subjects are not eligible for clinical study participation if they meet any of the following exclusion criteria:

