6.5 SCS TRIAL IMPLANT

During the trial implant, two SCS leads will be implanted using standard surgical techniques. One lead will be implanted using paresthesia mapping to maximize the overlap between painful regions and evoked paresthesia according to standard clinical practice. A second lead will be implanted using a novel anatomical midline-based placement. Under fluoroscopic guidance the lead will be positioned above the anatomical midline such that it extends over the T9-T10 junction. No tonic stimulation based paresthesia mapping will be performed to implant this lead. Leads will be connected to the EPG such that channels 1-8 will provide stimulation through the paresthesia mapping-based lead and channels 9-16 to the anatomical midline-based lead.

Subjects will be randomized 1:1 to either lead sequence (paresthesia lead first followed by anatomical lead or vice versa). Only stimulation programs using the lead selected by the randomization will be programmed in the EPG. When programming stimulation delivered with the lead implanted using the paresthesia-based placement, paresthesia mapping will be used to define the optimal contacts to activate. When programming stimulation delivered with the lead implanted using the anatomical-midline placement, a generalized bipolar stimulation approach will be used.

During the programming sessions, burst stimulation amplitude will be slowly increased up to the point where the subject feels any stimulation induced sensation (paresthesia, warmth, heaviness, cramping); this intensity value will constitute the Threshold for Perception (TP). Intensity will be then set at 60% of TP and the subject will be asked to move around, walk and cough. If sensations are still experienced, amplitude will be reduced in 0.05 mA steps until no sensations are experienced during the aforementioned activities. This intensity level will be used to define the target intensity and the stimulator will be programmed to allow the subjects to increase stimulation intensity up to 80% of TP. Subjects will be instructed to increase stimulation intensity slowly (by one click every two hours) if they are not experiencing pain relief. Similarly, intensity should be reduced slowly if they are experiencing increased pain, uncomfortable stimulation, heaviness or any other side effects.

Subjects will be provided with a pain diary, instructed to fill it daily and return it at the trial assessment visit 1.

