The following activities and assessments will be performed during SCS trial:

Timing of visit	Activities at visit	Case Report Form
SCS Trial	
SCS lead implantEPG programmingCollect stimulation parametersProvide pain diary	
• Surgery Form• Randomization Form• Programming Parameters Form• VAS Pain Diary Form

Clinical Investigational Plan

6.6 TRIAL ASSESSMENT 1

Two weeks after the start of the trial subject will assess therapeutic efficacy of the stimulation delivered using the lead assigned by randomization. Subjects will rate their level of pain using the VAS assessment, their quality of life using the EQ-5D questionnaire and their disability level using the ODI questionnaire.

Before any change is made, stimulation parameters used in the previous two weeks will be collected. Subsequently, subjects will cross over to stimulation delivered using the second lead. EPG stimulation programs used in the previous 2 weeks will be deleted and new stimulation programs will be programmed using the procedure detailed in the section 6.5.

Subjects will return the pain diary, be provided with a new one, instructed to fill it daily and return it at the trial assessment visit 2.

The following activities and assessments will be performed during end of anatomical lead trial visit:

Timing of visit	Activities at visit	Case Report Form
Trial Assessment 1	
Subject assessments of current pain levels, quality of life and disabilityCollect stimulation parametersEPG programmingCollect pain diaryProvide pain diary	
VAS FormEQ-5DODIProgramming Parameters FormVAS Pain Diary Form

6.7 TRIAL ASSESSMENT 2

At the end of the trial, subject will assess therapeutic efficiency of the stimulation delivered in the previous two weeks. Subjects will rate their level of pain using the VAS assessment, their quality of life using the EQ-5D questionnaire, their disability level using the ODI questionnaire and their preference. If the improvement in VAS obtained at either of the two trial assessment visits is $\geq 50\%$ of the baseline score, SCS trial will be considered successful and subjects will be considered for permanent IPG implant. Otherwise the subject will exit the study.

The following activities and assessments will be performed during end of anatomical lead trial visit:

Timing of visit	Activities at visit	Case Report Form

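### The study's only pass/fail rule (12.3) rests on undefined 'significant' relief with the anatomical-midline lead alone, so its verdict is not tied to the primary comparison with paresthesia mapping

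*Combined protocol and SAP*

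**What the plan says.** Section 12.3, headed as the pass/fail criteria for the results of the clinical study, consists of one sentence: "The trial will be considered successful if significant pain relief can be obtained using burst stimulation in leads implanted using anatomical midline-based lead positioning". No other study-level success rule appears. The 50% VAS reduction in 4.2 and 6.7 is a per-subject condition for permanent implant; it can be met on either lead, and 12.3 does not cite it.

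Section 4.1 begins "The primary purpose of this study is to compare the therapeutic efficacy of the conventional, paresthesia mapping-based burst SCS implant strategy" and sets that strategy against the AM approach. The only primary objective (4.3.1) is "Compare pain relief provided by paresthesia mapping-based burst trial to anatomical midline-based burst trial". Sections 4.2 and 6.5 randomise lead order 1:1. After two weeks on the first lead, "Subjects will then cross over to the second trial phase" (4.2); the switch is made at the Trial Assessment 1 visit (6.6), and no washout is described.

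The primary endpoint (4.4.1) is change from baseline in low back and lower limb pain. Section 12.1 names a repeated measures ANOVA but no hypothesis, contrast or significance level. Section 12.2 calls the study a feasibility trial, gives no power calculation, and says that the size was chosen for early evidence and effect-size estimates.

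**The concern.** The verdict and the primary objective ask different questions. The objective asks how AM compares with PM; 12.3 asks only whether AM gives relief.

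The two quantities are also protected differently. AM relief, presumably measured from baseline, is an uncontrolled before-after change in subjects selected for high pain: "Subject has a low back and pain intensity of at least 6.0 out of 10.0 on the VAS at baseline" (4.5.1). Regression to the mean, placebo response and the effect of the procedure would all count towards it. In the within-subject difference the shared baseline cancels, (AM − baseline) − (PM − baseline) = AM − PM, and the randomised order balances period effects. The protected contrast is the one that the verdict leaves out.

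Two consequences follow. The study could be called successful while its own crossover data show AM worse than PM, and nothing in 12.3 tells a reader that this label is separate from the primary objective. And because 'significant' is undefined, the height of the bar could be chosen after the data are seen. The time point is open too: a secondary objective in 4.3.2 looks at AM relief at 3, 6 and 12 months. By then the subjects on AM are those who passed the 50% gate on either lead and either preferred AM or had no preference.

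**Working it through.** **The plan's own figure.** Section 12.2 expects at least 80% of subjects to be implanted and stops enrolment at 40 implants: 40/0.80 = 50, matching the stated 50. If every trial succeeded, enrolment would stop at 40. Both n=50 and n=40 are therefore used below. The plan gives no power or alpha to reproduce.

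**Assumed inputs (none is in the documents).** SD of VAS change 2 to 3 points; AM/PM correlation ρ 0.3 to 0.7; two-sided 5% level; 'significant' read as p<0.05 for AM change against baseline; the true mean falls shown in the table.

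**Step 1: where the bar would sit.** Smallest observed mean AM fall that passes = t(0.975, n−1) × SD/√n.
- n=50: 2.010 × 2/7.071 = 0.57; 2.010 × 3/7.071 = 0.85.
- n=40: 2.023 × 2/6.325 = 0.64; 2.023 × 3/6.325 = 0.96.

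Against the entry floor of 6.0 this is 0.57/6.0 = 9% to 0.85/6.0 = 14% at n=50, and 11% to 16% at n=40.

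**Step 2: chance that 12.3 is met and AM is significantly worse.** Bivariate normal falls were simulated. The rule is met if the one-sample t for the AM fall exceeds t(0.975, n−1). AM is significantly worse if the period-adjusted crossover t for PM minus AM fall exceeds t(0.975, n−2). Ranges run over SD 2, 2.5, 3 and ρ 0.3, 0.5, 0.7.

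| True fall AM / PM | n=50 | n=40 |
|---|---|---|
| 1.5 / 3.5 | 0.91 to >0.99 | 0.81 to >0.99 |
| 3 / 4 | 0.50 to 0.99 | 0.41 to 0.98 |
| 3 / 3.5 | 0.16 to 0.61 | 0.14 to 0.51 |
| 3 / 3 | 0.02 to 0.03 | 0.02 to 0.03 |

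The last row is the one-sided 2.5% error rate, as it should be when the leads are equal.

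**Step 3: what the primary contrast can deliver at this size.** SD of the paired difference = SD × √(2(1−ρ)): 2 × √0.6 = 1.55 to 3 × √1.4 = 3.55. The 95% CI half-width is t(0.975, n−2) × SDd/√n.
- n=50: 2.011 × 1.55/7.071 = 0.44 to 2.011 × 3.55/7.071 = 1.01 points.
- n=40: 2.024 × 1.55/6.325 = 0.50 to 2.024 × 3.55/6.325 = 1.14 points.

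A first-period comparison (25 subjects per sequence at n=50) has half-width 2.011 × SD × √(2/25): 1.14 points at SD 2 and 1.71 at SD 3. It is usable as a sensitivity check, not as the main estimate.

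**The case against.** The strongest reply is that this is a feasibility study. Section 2.0 says that the efficacy of burst stimulation through AM leads is unknown, and 3.8 gives AM's expected advantages as procedural: shorter surgery and steady sedation. Whether AM works at all is then a sensible go/no-go question, and a technique can be worth pursuing even if it relieves somewhat less pain. This stands. In the 3 / 4 row of the table, AM's true fall is already 50% of the 6.0 entry floor, which many would call a real feasibility success. Only the 1.5 / 3.5 row clearly shows a weak technique passing, and that pair is an assumption.

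A reader might go further and infer that the AM versus PM comparison has been dropped. The documents do not support that: it remains the primary objective, and the ANOVA in 12.1 could serve it. Nor does 12.3 drive patient care; the activated lead follows subject preference (4.2, 6.9).

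A reader might also set the 0.57 to 0.85 points against 3.0 points (50% of 6.0) and conclude that the plan holds two bars several-fold apart. That overreaches, because the 50% figure is a per-subject gate and the other is a threshold for a group mean.

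What the reply does not answer is that 12.3 presents the feasibility answer as the result of the whole study, and that the rule cannot be applied until 'significant' is defined.

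**Conclusion.** The point holds as a mismatch in the verdict rule. Section 12.3 ties success to AM relief alone, leaves the bar undefined, and does not say that this is separate from the primary objective. That conclusion rests on the text and needs no figure.

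The size of the consequence rests wholly on assumed SDs, correlations, effects and one reading of 'significant'. It is large only if AM is truly worse by about a point or more, and falls to 0.02 to 0.03 if the leads are equal. The documents do not say which case applies, so it should not be inferred that a misleading verdict is likely. They also do not support a claim that a single-technique criterion is wrong in itself, or that a non-inferiority margin is missing: the stated aim is to compare.

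The trial data remain fully analysable. This is a cheap improvement to the plan.

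**What to change.** **In 12.1, name the primary contrast.** The within-subject AM minus PM difference in VAS change from baseline at the trial assessments, with two-sided 95% CI, from a crossover model with lead, period and sequence terms and subject as random effect, in all randomised subjects with at least one trial assessment. Take low back pain first, since the population is defined by it, and report lower limb pain alongside. State that unequal carry-over would bias this contrast because no washout is described, and give the first-period comparison as a sensitivity analysis.

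**Replace 12.3 with:**

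> Feasibility criterion, not a test of the primary objective: mean change from baseline in low back VAS at the end of the AM phase, same analysis set. It is met if the lower 95% confidence limit of the mean fall exceeds a number fixed before any outcome data are accessed. It is reported beside the AM minus PM estimate and CI, and meeting it supports no claim that AM is comparable to PM.

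The number should be fixed before data access, not merely before unblinding: 4.2 describes blinding of subjects, no blind for the analyst is described, and sponsor personnel enter the data (9.1).

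**Cost.** Wording and one named contrast. VAS is already collected at both trial assessments. Subjects without a successful trial leave only after the second ("Otherwise the subject will exit the study", 6.7), so no extra visit or patient is needed. The price is that meeting the AM criterion can no longer be reported as success on the primary objective, and the AM minus PM interval may be wide, as step 3 shows.
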